1 CCI

CCI

CCI

CCI

CCI

CCI

This study is descriptive and there will be no formal hypothesis testing for the primary objective.

Methods:

Study design: This community program intervention study will examine the process of integrating the AIRQ™, Asthma Checklist, and educational resources (PRECISION program) into clinical practice using either in-person or telehealth visits. Providers use of patients' responses to the AIRQ™, Asthma Checklist, and educational resources to guide treatment and asthma work-up and management also will be examined. The study duration is 12-months, with study enrollment lasting nine (9) months for each site (implementation stage), and an additional three (3) months of follow-up to assess the sustainability of using the PRECISION

Observational Study Protocol Form

Version 3.0

Form Doc ID: AZDoc0059948

Parent Doc ID: SOP LDMS_001_00164328

program in clinical practice (sustainability stage). The nine-month implementation stage will allow for the recruitment of approximately 50 patients at each site for an initial study visit, plus the potential for follow-up visit(s). The three-month sustainability stage will allow for sites to continue to implement the PRECISION program in their clinical practice and for sites to describe any continued benefits of using the PRECISION program at their site.

Approximately fifteen (15) to twenty (20) clinical sites will be recruited to participate in this study, categorized into the following three practice clusters: (1) primary care site (e.g., private practice, FQHC; (2) specialty care site (pulmonary, asthma/immunology); and (3) novel sites (e.g., pharmacy, nurse practitioners, nurse educators, prescribers and Non-prescribers, telehealth component of Allergy and Asthma Network). While all sites will be able to conduct both in-person and telehealth visits, sites will aim to conduct a minimum of approximately 25% of their initial patient visit using a telehealth platform. Both platforms (in-person and telehealth) can be used for the follow-up visit(s) for all practice types.

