4.1.2 AIRQ™

The AIRQ™ (Appendix E) consists of 10 yes/no items, with the total score used to identify patients at risk for poor asthma outcomes. The AIRQ™ questions address medication use, asthma symptoms, exacerbations, unscheduled medical telehealth visits, hospitalizations, and asthma-related impairment. The majority of AIRQ™ items use a two-week recall period (questions 1 through 7), while the risk items use a recall period of the prior 12 months. The AIRQ™ is available in English and Spanish (Appendix F); both versions will be used in this

study. The AIRQ™ is also available in a 3-month recall version in English (Appendix G) and Spanish (Appendix H).

Sites will be asked to ensure that the AIRQ™ is completed before the patient sees the HCP. For in-person visits, the AIRQ™ can be completed by the patients on paper (self-administration) or completed by site staff as interviewer-administered. For telehealth visits, the AIRQ™ can be sent to patients in advance of the visit (e.g., sent via email as a PDF or sent via a link to www.digitalairq.com) and completed by the patients on paper (self-administration) or completed by site staff as interviewer-administered. In the case that the patient receives the AIRQ™ in advance of their visit, the patient can provide their responses on the self-completed AIRQ™ to the site staff who will then transpose patient responses to the CRF paper version of the AIRQ™ and provide to the HCP at the start of the visit. Examples of ways to administer the AIRQ™ during a telehealth visit will be provided as part of the site training.

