4.3 Other Variables and Covariates

Additional variables and covariates may be examined based on the availability of data. A more detailed description of additional variables and covariates will be included in the Statistical Analysis Plan.

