- During the visit, how was the AIRQ™ administered?
 Interviewer Patient self-completed
- During the visit, was the patient able to see their risk score on the ruler included in the AIRQ™?
 Yes No

IF yes, how were patients able to view their risk score?

On their phone
 On their computer
 Paper copy of AIRQ™ mailed to patient before the visit or provided at in-person visit
 Other, please specify: _____

- Age (years): 

Evidera 138	Site	Page 3 of 7
		
Evidera # 138	Plate # 003	Visit # 001
Participant ID		

5. Sex: male female non-binary Other: _____

6. How would you rate this patient's asthma severity?
 Intermittent
 Mild persistent
 Moderate persistent
 Severe persistent

[figure not shown]
7. Age of asthma diagnosis:  Unknown

8. What is your assessment of the patient's overall asthma control?
 Completely controlled
 Well controlled
 Somewhat controlled
 Poorly controlled
 Not controlled

9. Did the patient previously have COVID or do they currently have COVID?
 Yes No Unknown

10. What type of health insurance coverage does the patient have? (Check all that apply)
 Third-party payer (for example, United Healthcare, Blue Cross/Blue Shield, Aetna)
 Managed care organization
 Tricare (military health insurance)
 Affordable Care Act (ACA)
 Medicare
 Medicaid
 Self-pay
 None
 Other (please specify): _____

11. Patient's state of residence: 

Evidera 138	Site	Page 4 of 7
		
Evidera # 138	Plate # 004	Visit # 001
Participant ID 		

12. Please indicate the medication the patient has taken for the past 3 months:

[figure not shown]
MAINTENANCE PHARMACOLOGIC THERAPY Please check all that apply .	

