[REDACTED] [REDACTED] [REDACTED] [REDACTED] Descriptive statistics (n, %) will be presented for the ACE Questionnaire (item scores) by practice cluster, visit platform, AIRQ® control score, exacerbation history, education level, language, age, sex, and NEPP step level (Table 7 series). Item responses and scores on the patient-reported outcome measures (AIRQ®, CCI [REDACTED] and ACE) will be compared across groups (practice cluster, visit platform, exacerbation history, education level, language, age, sex and NAEPP step level). For continuous variables, ANOVA will be used to compare mean scores across groups; pairwise comparisons between means will be performed using Scheffe's test adjusting for multiple comparisons for more than two groups. For categorical data, chi-square analyses will be used to compare frequencies by groups. No adjustments will be made for multiple groups.

For the follow-up analysis dataset, a patient disposition table will be developed to descriptively characterize the follow-up analysis set in terms of age group, language, race, and education by practice cluster (Table 8a). The mean time to first follow-up visit will be described (n, %) in Table 8b. For the primary care and specialty clusters, the first follow-up clinical CRF will be completed at the patient's first follow-up visit. For the novel cluster sites where patients are receiving multiple asthma coaching sessions, the follow-up clinical CRF will be completed at their final coaching session.

Descriptive statistics (n, %) will be used to describe patients with a follow-up visit by AIRQ® control level at initial visit (Tables 8c). Descriptive statistics (n, %) will also be used to describe patients with a follow-up visit by exacerbation history, education level, language, age, sex, and NAEPP step level at the initial visit (Tables 8d to 8i). Descriptive statistics (n, %) will be used to describe patients with a follow-up visit by HCP actions at the initial visit overall and by practice cluster (Table 8j to 8m).

Clinical characteristics and visit information from the first follow-up visit will be presented using descriptive statistics (n, mean [SD], median, range) (Tables 9a to 9e). Descriptive statistics (n, mean [SD], median, range) will also be used to present the results (overall and by practice cluster) for the first follow-up AIRQ® scores and control levels (Table 10a). AIRQ® scores from the first follow-up

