Appendix B. Revisions to Select Analyses Initially Detailed in this SAP

Due to the nature of the data collected or to enhance clarity of presentation or interpretation of findings, some revisions were made to select analyses initially specified in the SAP. These revisions are detailed below:

- Novel site results were displayed in separate tables (N table series)
- All analyses by language were not conducted since the AIRQ was only administered in English language.
- There was no data on PRECISION education resource views/downloads for the specialty care cluster so tables 22c and 23c could not be run
- Some analyses could not be conducted due to the small sample size, e.g., for Tables 23e-23j, Tables 29b1-b3, Tables 29e-t, Table 30a, Table N4d, Tables N6b-N6i, Tables N7b-N7i, Table N8e, N10d, N22f, N23e, N29e-N29t or due to lack of data (i.e., no telehealth visits **CCI** or medical record history data available for the novel site so Table N3c, N4b, N4c, N5, N8d, N9b, N10b, N10c, N22e, N23e could not be presented).
- There was only one follow-up visit per patient so some analyses could not be presented (Table 24 and Table N24 series) or were modified (Table 25)
- Some tables duplicated content from other tables and are not presented (content for the Table 26, 27, N26 and N27 series can be found in the Table 20, 21, N20 and N21 series)
- Inferential statistical tests (e.g., ANOVA, chi-square test) were run to determine if differences between the practice clusters were statistically significant for Table 3e and Tables 8 series, Tables 10 series, Table 20 series
- A Bowker's test was used instead of a Cochran's Q test to evaluate if there were within-patient changes in OCS use (Table 31b) as the Cochran's Q test was not suitable 9 (only provides a method for testing three or more binary matched pairs).

Statistical analysis plan
D2287L00028 (EVA-26645)

AstraZeneca
27 Sep 2023

SIGNATURES

ASTRAZENECA SIGNATURES

D2287L00028 PRECISION Study 4 – Implementation

Statistical Analysis Plan for the Implementation of the US PRECISION AIRQ®,
Asthma Checklist, and Educational Resources (PRECISION Program) into
Clinical Practice Using Telehealth and In-Person Platforms: Addendum

This statistical analysis plan addendum has been subjected to an internal AstraZeneca review.

I agree to the terms of this statistical analysis plan.

AstraZeneca Study Statistician

PPD

Evidera Statistical Oversight

PPD

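### Telehealth and in-person results on ACE and AIRQ are tested without adjustment, although platform is not allocated and its share may differ between sites

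*SAP*

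**What the plan says.** SAP 5.1 plans that responses and scores on AIRQ, ACE and a redacted measure "will be compared across groups (practice cluster, visit platform, exacerbation history, education level, language, age, sex and NAEPP step level"). The methods are "For continuous variables, ANOVA will be used to compare mean scores across groups", and "For categorical data, chi-square analyses will be used to compare frequencies by groups. No adjustments will be made for multiple groups". The last sentence concerns multiplicity. It is not a statement about covariates.

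Protocol 4.3 deferred covariates: "A more detailed description of additional variables and covariates will be included in the Statistical Analysis Plan". SAP 4.3 then lists only practice cluster, as a way of describing the sample. SAP 4.2.2 commits the secondary results to presentation by cluster and platform.

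On how platform arises, the protocol synopsis says "sites will aim to conduct a minimum of approximately 25% of their initial patient visit using a telehealth platform". Protocol 3.1 repeats this and says that all sites can run both kinds of visit. SAP 2 keeps both platforms at sites without repeating the minimum. Neither document gives a rule for which patients are seen by telehealth.

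On mode, Protocol 4.1.2 describes the AIRQ in the same words for in-person and telehealth visits: "completed by the patients on paper (self-administration) or completed by site staff as interviewer-administered". The Clinical CRF (Protocol Appendix I, Part 3, item 2) records which was used: "Interviewer Patient self-completed".

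The bias sections (Protocol 5.2.1, SAP 6.1) mention selective ACE response and selection into follow-up. They do not mention selection into platform or administration mode.

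**The concern.** An unadjusted two-group test attributes the whole difference to the grouping factor. Here that factor is chosen by sites and patients. Clinics that use more telehealth may treat milder or more severe asthma, or give visits that patients rate differently. Within a clinic, the patients seen remotely may differ from those who attend. For AIRQ, answers given to an interviewer may also differ from answers written down alone.

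The study implements the program on both platforms, and the secondary results are to be shown by platform. A p-value beside that contrast invites the reading that telehealth changes scores or visit experience. The unadjusted test cannot separate that from the mix of sites and patients.

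**Working it through.** **The plan's own figure.** The only stated quantity is the sample size of about 750 to 1,500 from 15 to 20 sites, with a target of 50 and a cap of 75 per site (SAP 2 and 2.1). 15 × 50 = 750 and 20 × 75 = 1,500, so it reproduces. No alpha, effect size, SD or ICC is given. Everything below is in SD units, two-sided at 0.05.

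**Sensitivity of the platform contrast.** Assume 25% telehealth and independent patients. The difference detectable with 80% power is (1.960 + 0.842) × √(1/n₁ + 1/n₂).

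- N = 750: 2.802 × √(1/187.5 + 1/562.5) = 0.24 SD.
- N = 1,500: 2.802 × √(1/375 + 1/1,125) = 0.17 SD.

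These use all enrolled patients. ACE is optional, so its numbers will be smaller and its detectable difference larger.

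**Site confounding, closed form.** Let p be the mean telehealth share, s the SD of shares across sites, and r the correlation of share with site mean. With no true platform effect, the expected unadjusted difference is r × s × √ICC / [p(1 − p)]. Assume p = 0.25, so p(1 − p) = 0.1875, and r = 0.5.

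- s = 0.10, ICC = 0.02: 0.5 × 0.10 × 0.141 / 0.1875 = 0.04 SD.
- s = 0.20, ICC = 0.10: 0.5 × 0.20 × 0.316 / 0.1875 = 0.17 SD.
- s = 0 or r = 0: zero.

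The 25% is a minimum, so the true mean share may be higher. At p = 0.40, p(1 − p) = 0.24 and each bias is multiplied by 0.1875 / 0.24 = 0.78.

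**Site confounding, simulation.** There was no true platform effect and 1,500 runs per setting, for 15 × 50 and 20 × 75 patients, ICC 0.02, 0.05 and 0.10, and mean share 0.25. Setting (a) fixes s at 0; settings (b) and (c) use s of 0.10 and 0.20.

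| Setting | Unadjusted bias (SD) | Unadjusted false positives | With site fixed effects |
|---|---|---|---|
| (a) every site at 25% | about 0 | 3.7%–4.9% | 4.9%–5.4% |
| (b) shares vary, r = 0 | about 0 | 5.3%–21.2% | 4.1%–5.9% |
| (c) shares vary, r = 0.5 | 0.03–0.16 | 7.9%–64.7% | 4.3%–5.7% |

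With site fixed effects the mean bias was at most 0.004 SD in every setting. The simulation error at 5% is √(0.05 × 0.95 / 1,500) = 0.56 percentage points, so the adjusted rates are compatible with 5%. The excess in (b) is a clustering effect on the standard error; only (c) is bias in the estimate.

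**Administration mode (AIRQ).** Bias = gap in interviewer share between platforms × mode effect. An assumed gap of 0.2 to 0.6 and effect of 0.1 to 0.3 SD give 0.2 × 0.1 = 0.02 to 0.6 × 0.3 = 0.18 SD. With no gap it is zero.

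The calculations use a continuous score. They show the mechanism for ACE items but do not model their four categories.

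**The case against.** The strongest reply is that no platform effect is a stated target. The primary objective is descriptive and rests on the provider survey, interviews and touchpoint calls. Protocol 5.1.2 makes platform one of several subgroup analyses that may be done. The initial AIRQ is completed before the patient sees the provider and asks about the past 2 weeks and 12 months. Apart from mode, the visit platform cannot cause that score, so the comparison describes who used telehealth. This stands, and it is why ACE is the outcome for which a platform effect is meaningful. It does not clear the tests: the descriptive label covers the primary objective only, and SAP 5.1 specifies inferential tests for these measures.

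Four stronger readings are tempting and are not supported:

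- A reader might infer that platform is set by site. Both platforms are planned at every site, and site confounds only as far as shares vary together with site means.
- A reader might infer that platform is tied to how the AIRQ was given. Both modes are allowed on both platforms; a difference is possible but not documented.
- SAP Appendix B lists novel-site tables not presented "due to lack of data (i.e., no telehealth visits". A reader might take this as proof of bias in the main tables. The same appendix places novel results in separate tables.
- The sentence on no adjustment for multiple groups might be read as ruling out covariates. It concerns multiplicity.

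It is also fair that redacted exploratory sections might contain models. The method sentences for this comparison are readable, however, and name none.

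**Conclusion.** The point holds in a limited form. The platform tests on ACE and AIRQ are unadjusted, platform is not allocated, and its share may differ between sites, so the p-values can reflect site and patient mix. For AIRQ they can also reflect administration mode.

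Whether bias occurred, and in which direction, cannot be told from the documents. It ranges from nil (equal shares, or shares unrelated to site means) to about 0.16 SD from site alone under the assumptions above. That upper value is close to the 0.17 SD detectable with 1,500 patients. The ICC, spread of shares, correlation and mode effect are all assumed. This is a worthwhile, inexpensive improvement to a secondary comparison. It does not affect the primary objective.

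**What to change.** **ACE items.** Replace the unadjusted platform test with one stratified by site, such as a Cochran-Mantel-Haenszel row-mean-score test, or with an ordinal model containing platform and site as a fixed effect. Site adjustment leaves case mix within a site untouched. A model-based version should therefore add baseline covariates already on the CRF: age, provider-rated severity and exacerbation history.

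**Initial AIRQ.** Either show platform means as description without a p-value, or fit a linear model with site fixed effects, platform, administration mode (Clinical CRF Part 3, item 2) and the same covariates. Report the within-site difference with a 95% CI.

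**Labelling.** SAP Appendix B reports analyses already run, so call this a supplementary analysis. Name selection into platform and administration mode as limitations in SAP 6.1.

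**Cost.** SAP wording and one extra analysis per platform table, with no new data collection. Sites with only one platform contribute nothing to the contrast, and the confidence interval will be somewhat wider. Selective ACE response, already acknowledged in SAP 6.1, would remain.

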2. STUDY DESIGN AND SAMPLE SIZE

This community program intervention study will examine the process of integrating the AIRQ®, Asthma Checklist, and educational resources (PRECISION program) into clinical practice using in-person or telehealth visits. Providers' use of patients' responses to the AIRQ®, Asthma Checklist, and educational resources to guide treatment and asthma work-up and management will be examined. All participants will be enrolled in the study by February 2022. Study duration for each site will be 12 months, including a nine month study implementation phase (starting when the last patient is enrolled at the site) and an additional three months of follow-up to assess the sustainability of using the PRECISION program in clinical practice (sustainability stage). The nine-month implementation stage will allow for potential follow-up visits for each enrolled patient. The three-month sustainability stage will allow for sites to continue to implement the PRECISION program in their clinical practice and for sites to describe any continued benefits of using the PRECISION program at their site.

Approximately 15 to 20 clinical sites will be recruited to participate in this study, categorized into the following practice clusters: (1) primary care site (e.g., private practice, FQHC; 2) specialty care site (pulmonary, asthma/immunology); and (3) novel sites (e.g., pharmacy, nurse practitioners, nurse educators, prescribers and non-prescribers, telehealth component of Allergy and Asthma Network).. Sites will be able to conduct in-person and telehealth visits for initial and follow-up visit(s).

During the clinic visit (telehealth or in-person), HCPs will assess the patients' responses to the AIRQ® questions, discuss the results with the patient, and use the Assess component of the Asthma Checklist (as appropriate per HCP judgment). Before completing the initial study visit, patients will be asked if they would be willing to complete additional questions and, for those who agree, sites will send them an electronic survey link (via YouGov) that will include the following questionnaires: the Asthma Clinic Experience (ACE) Questionnaire, [CCI](#)

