4.3 Other Variables and Covariates

The sample will be characterized by practice cluster: (1) primary care sites (e.g., private practice, FQHC); (2) specialty care sites (pulmonary, asthma/immunology); and (3) novel sites (e.g., pharmacy, nurse practitioners, nurse educators, prescribers and non-prescribers, telehealth component of Allergy and Asthma Network).

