5. ANALYSIS METHODS

5.1 Statistical Methods – General Aspects

An overall data disposition figure (Figure 1) will be generated on all enrolled patients to describe total enrolled/consented, total sample included/excluded from analyses, and finally key data (AIRQ®) availability status. In the data disposition figure, the total sample who had a follow-up visit will be reported by practice cluster. A patient disposition table will also be developed to descriptively characterize the sample in terms of total patients enrolled, age group, and language by site and practice cluster (Table 1a to Table 1c). Descriptive statistics (n, frequency, mean, median, and SD) will be used to characterize the sample in terms of the patient-reported sociodemographic and clinical characteristics (e.g., age, sex, education, etc.) (Table 2a and Table 2b, respectively), overall and by practice cluster. Descriptive statistics (n, frequency, mean, median, and SD) will be used to characterize the sample overall and by cluster type in terms of clinician-reported patient characteristics, clinical characteristics, and visit information (Tables 3a to 3f).

Descriptive statistics (n, mean [SD], median, range) will also be used to present the results (overall and by practice cluster) for the AIRQ® total and control level scores (Table 4a). AIRQ® scores will also be summarized by visit platform (telehealth vs. in-person), exacerbation history, education level, language (sample size permitting), age, sex and NAEPP step level (Table 4b to 4h). Descriptive statistics (n, mean, SD, median range) will be presented for CCI [REDACTED]

[REDACTED] Descriptive statistics (n, mean [SD], median, range) will be presented for CCI [REDACTED]

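### Practice-cluster p-values treat patients as independent, although practice cluster is a property of the site, so they are too small when outcomes correlate within site

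*SAP*

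**What the plan says.** Practice cluster is defined at site level. SAP section 2: "Approximately 15 to 20 clinical sites will be recruited to participate in this study, categorized into the following practice clusters". SAP 4.3 repeats it: "The sample will be characterized by practice cluster: (1) primary care sites", followed by specialty and novel sites. Protocol 5.3 expects about 3 to 5 sites in each cluster.

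SAP 5.1 then compares patient-reported responses and scores across several groupings, practice cluster among them. "For continuous variables, ANOVA will be used to compare mean scores across groups"; Scheffe's method is used for pairs when there are more than two groups. "For categorical data, chi-square analyses will be used to compare frequencies by groups".

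SAP Appendix B records what was done: "Inferential statistical tests (e.g., ANOVA, chi-square test) were run to determine if differences between the practice clusters were statistically significant". It names Table 3e and the Table 8, 10 and 20 series. It also moves the novel-site results to their own N tables and, when listing missing data, writes of "medical record history data available for the novel site" in the singular.

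No readable part of either document names a site effect, mixed model, GEE, cluster-robust variance, design effect or ICC. Site appears only as a level for descriptive summary or stratification. The bias sections (Protocol 5.2.1, SAP 6.1) cover ACE response bias and selection into follow-up, not correlation within site.

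**The concern.** All patients at a site share its practice cluster, so the cluster contrast is made entirely between sites. The patient-level ANOVA judges it against the pooled spread of patients within a cluster and counts each patient as independent information. If patients at one site resemble each other, through case mix, staff or the way the AIRQ is administered, the cluster means vary more than that error term allows. Scheffe's method uses the same error term; it protects against many contrasts, not against correlation within site. The chi-square test makes the same independence assumption.

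At stake is whether a difference between practice types reported as significant is only ordinary site-to-site variation. Such correlation is plausible: Protocol 3.1.1 selects sites partly for the diversity of their patients and for what is unique about each site, and one cluster mixes private practices with FQHCs.

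The scope is the practice-cluster p-values only. Comparisons by factors that vary among patients within a site, such as sex, are affected much less, provided the factor is spread similarly across sites. The Table 20 series cannot be assessed because the exploratory sections are redacted.

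**Working it through.** **Plan's own figure.** 15 sites × 50 patients = 750 and 20 × 75 = 1,500, which reproduces the stated range of 750 to 1,500. (20 × 50 gives 1,000, so the upper end needs the 75-patient cap of SAP 2.1.) The plan states no alpha, power or ICC for cluster contrasts.

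**Inputs.**
- From the documents: 50 patients per site (SAP 2.1); 3 to 5 sites per cluster (Protocol 5.3).
- Assumed: alpha 0.05; ICC 0.01, 0.02, 0.05 and 0.10; 10 patients per site with follow-up; 20 ACE responders per site.
- Number of clusters tested: two is likely for the main tables, since novel results went to the N tables; three is what SAP 5.1 planned.

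**Formula.** With m patients per site, the variance of a cluster mean is inflated by DE = 1 + (m − 1) × ICC. The true error of the nominal 5% test is approximately P(χ²_df > c/DE), where c is the 5% critical value and df is the number of clusters minus 1.

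Example with two clusters, m = 50, ICC 0.02: DE = 1 + 49 × 0.02 = 1.98; 3.841/1.98 = 1.940; P(χ²₁ > 1.940) = 0.164.

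| True error of a nominal 5% test | ICC 0.01 | 0.02 | 0.05 | 0.10 |
|---|---|---|---|---|
| DE, m = 50 | 1.49 | 1.98 | 3.45 | 5.90 |
| Two clusters, m = 50 | 11% | 16% | 29% | 42% |
| Three clusters, m = 50 | 13% | 22% | 42% | 60% |
| Two clusters, m = 10 | 6% | 7% | 10% | 16% |
| Three clusters, m = 10 | 6% | 8% | 13% | 21% |

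With two clusters the true error reaches 10% when DE = 3.841/2.706 = 1.42, that is at ICC 0.42/49 = 0.009 for m = 50 and 0.42/9 = 0.047 for m = 10.

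**Simulation under the null** (normal random site effect, 5 sites per cluster, 10,000 runs). Patient-level ANOVA, two clusters, m = 50: 11.0%, 16.8%, 30.2%, 42.9%. With 3 sites per cluster: 11.0%, 16.7%, 28.7%, 42.1%, so the number of sites hardly matters. With uneven sites (10/25/50/75/90 in each cluster): 12.6%, 19.9%, 35.4%, 48.1%. With three clusters, at least one Scheffe pair was significant in 4.0% of runs at ICC 0, 19% at 0.02 and 38% at 0.05 (4,000 runs).

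**Chi-square, ICC on a latent normal scale** (4,000 runs, response shares assumed).
- AIRQ control level (35/35/30%), two clusters: 8%, 11%, 22%, 32% at m = 50; 5%, 6%, 8%, 12% at m = 10.
- ACE item (40/45/11/4%), m = 20: 5%, 7%, 11%, 17% with two clusters; 6%, 8%, 13%, 23% with three.

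If the ICC is placed on the observed scale of a binary item with p = 0.5, two clusters at m = 50 give 12%, 18%, 30%, 43%. The two sets are not comparable at the same nominal ICC.

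**With site as the error unit.** ANOVA on site means rejects in 4.7–5.2% of runs with equal sites and 4.1–4.8% with the uneven sites. ANOVA on site proportions gives 4.4–5.3%.

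**The case against.** The best counter-argument is about the target. If the p-values refer only to patients at the selected sites, site effects are fixed and the patient-level test is sound: with equal cluster means at those particular sites, a simulation (two clusters, 5 sites each, 50 per site) rejected 4.7%, 5.6%, 5.0% and 3.7% at the four ICCs. The SAP does not state its target, and Protocol 5.2.3 already doubts that the sites represent US practice. This stands as a condition on the finding. But a significance statement about differences between practice clusters will be read as one about practice types, and if the target really is these sites only, description without p-values serves it.

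Little depends on these tests. The primary objective is descriptive. The initial AIRQ is completed before the patient sees the HCP (Protocol 6.1.2), so a cluster difference there is case mix, not program effect. Table 3e describes patients or visits, and the Table 8 and 10 series concern patients with follow-up, where inflation may be mild. ACE is the readable experience outcome with a planned cluster test, but Appendix B does not list it among the added tests. All this limits the reach without removing the error. Nor does the descriptive label excuse it: the statement ruling out hypothesis tests in SAP 1.1 covers only the primary objective, and Protocol 5.3 goes further and disclaims inferential statistics, yet tests were run.

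The size is uncertain: ICC, follow-up numbers and ACE response per site are all assumed, and the three-cluster rows may not match what was run.

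Unweighted site means are not always safe either. In a deliberately extreme case (7 sites of 25 against 3 sites of 3) site-mean ANOVA rejected 18%, 17%, 14% and 11%, worse than the patient-level test (5%, 6%, 7%, 9%). With moderate imbalance (7 sites of 60 against 5 of 25) it held at 5.1–5.9%. This is a caveat on the remedy.

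**Conclusion.** The concern holds. The practice-cluster tests use the wrong error unit, and their p-values are too small whenever the ICC is positive and the inference is to practice types. For the likely two-cluster comparison, true error is about 11% to 42% at 50 patients per site and 6% to 16% at 10 per site over ICC 0.01 to 0.10. The direction is firm under those two conditions; the size is not, because it rests on an assumed ICC and, for follow-up and ACE, on assumed numbers per site. The effect is confined to the practice-cluster p-values. It should be fixed because significance tests between clusters were carried out and the correction is cheap.

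**What to change.** For practice-cluster contrasts, state the target of inference and choose one of two options.

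1. **Descriptive only.** Give estimates by cluster without p-values. This is the default if the target is only these sites, if a cluster has a single site (as Appendix B's wording on the novel site may imply), or if a cluster has only about 3 sites.
2. **Site as the error unit.** For the AIRQ score, use a random-intercept model for site with Kenward-Roger degrees of freedom, or ANOVA on site means. For ACE items and AIRQ control level, use ANOVA on site proportions (for example, percent agreeing or strongly agreeing; percent well-controlled). Site-level summaries weight sites equally, so say so, and avoid them where site sizes differ sharply between clusters. A permutation test of whole sites needs enough sites: its smallest two-sided p, 2/C(2k, k) for k sites per cluster, is 0.10 for 3 versus 3, 0.029 for 4 versus 4 and 0.008 for 5 versus 5.

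With either option, report the number of sites per cluster; with option 2, report the ICC as well.

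**Cost.** Option 1 only removes p-values. Option 2 is re-analysis of recorded data plus SAP wording. Intervals widen by √DE × t(0.975, 2k − 2)/1.96. For ICC 0.01 to 0.10 with two clusters:

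| Sites per cluster | m = 50 | m = 10 |
|---|---|---|
| 3 (4 df) | 1.73–3.44 | 1.48–1.95 |
| 5 (8 df) | 1.44–2.86 | 1.23–1.62 |
| 7 (12 df) | 1.36–2.70 | 1.16–1.53 |

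The last row applies if nearly all of the 15 to 20 sites fall in two clusters. Fewer differences will be nominally significant. Changes to the paired t-tests or to the visit-platform comparison are optional and not part of this point.
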